4.5.4 Concomitant Medications

Subjects may receive medications as supportive care or to treat AEs as deemed necessary by the investigator or the subject's physician. The use of pre-medication prior to administration of MEDI-551, in the absence of a previously documented reaction to MEDI-551, is permitted when it is clinically indicated or in accordance with institutional guidelines for administration of a MAb. Premedication with acetaminophen, diphenhydramine, and corticosteroids is mandatory before the first MEDI-551 infusion for Arms B, C, and D. The infusion rate should be reviewed and adjusted to minimize infusion reactions as detailed in Section 4.5.3. In addition, the following concomitant medications are allowed: 1) hematopoietic growth factors to treat anemia and cytopenias as per usual institutional practice following consultation with the Medical Monitor; 2) red cell and platelet transfusions in subjects who

are transfusion-dependent; 3) prophylactic intravenous Ig to prevent infections; 4) intrathecal prophylaxis with either methotrexate or cytarabine, if clinically indicated; and 5) prophylactic antibiotics. No transfusions are permitted during the DLT period for all dose-escalation cohorts in Arms B and C. For subjects with large tumor burden or elevated LHD (ie, at high risk for tumor lysis syndrome), prophylaxis against tumor lysis syndrome may be given according to institutional guidelines prior to initiation of study treatment (eg, hydration, urine alkalinization, administration of hypouricemic agent). Subjects' hydration status should be assessed to reduce risks of infusion-related hypotension; laboratory abnormalities that could complicate management if tumor lysis syndrome were to develop should be managed according to institutional standards.

All concomitant medications given to the subject from the time the subject signs the informed consent form through 90-Day Post Last Dose Visit will be recorded on the source document.

4.5.5 Dose Escalation

Rules for dose escalation in Arms A, B, and C are described below. This section is not relevant to Arm D.

Arm A

1. The MTD was to be determined based on the assessment of DLT during the DLT period (see Section 4.5.6). Subjects were considered evaluable for assessment of DLT if they received at least 1 full cycle (4 doses for Cohorts 1 and 2; 2 doses for Cohorts 3 to 6) of MEDI-551 and completed the safety follow-up through the DLT evaluation period, or experienced any DLT. Non-evaluable subjects were to be replaced. Any MEDI-551 treatment-related toxicity (regardless of grade) leading to an inability to receive a full cycle of MEDI-551 was to be considered a DLT.
2. Per protocol Version 4.0, dose escalation was initiated in 3 subjects with FL or MM treated at the 0.5 mg/kg dose, once a week for 4-week cycles. No DLTs were observed in the first 3 subjects during the DLT period; therefore, enrollment in the next higher dose cohort (Cohort 2) began. Subjects in Cohorts 1 and 2 continued to receive MEDI-551 weekly in 4-week cycles.
3. If no DLTs are observed in Cohort 2, dose escalation into Cohort 3 will proceed with enrollment of subjects with advanced B-cell malignancies (CLL, DLBCL, FL, or MM). If a DLT is observed in Cohort 2, expansion and evaluation will occur per Rule 5 below. Three subjects will be treated at the Cohort 3 dose on Days 1 and 8 in the 1st cycle (loading doses) and then once every 28 days at the start of each subsequent cycle. If no DLTs are observed in the first 3 subjects during the DLT period, enrollment in the next higher dose cohort will begin.

4. For the first two dose cohorts only, subject enrollment was staggered so that no fewer than 7 days (including the day of treatment of the first subject) separates treatment start dates for each subject. A staggered enrollment achieves an observation period between subjects such that an adequate safety evaluation, including the assessment for cytokine release syndrome and tumor lysis syndrome, could be performed prior to entry of additional subjects. If no Grade ≥ 2 cytokine release syndrome or tumor lysis syndrome was observed in the subjects in the first two cohorts during the first 7 days of treatment, enrollment and treatment of subjects in subsequent cohorts (Cohorts 3 and higher) was allowed to proceed concurrently.
5. If 1 of 3 subjects in a dose cohort experienced a DLT during the DLT period, that dose cohort was allowed to be expanded to a total of 6 subjects. If 1 of 6 subjects experienced a DLT, dose escalation continued in the next higher dose cohort.
6. If ≥ 2 subjects in a dose cohort experienced a DLT during the DLT period, the MTD would have been exceeded and no further subjects would be enrolled into that dose cohort. If this occurred, the preceding dose cohort would be evaluated for the MTD and a total of 6 subjects would be treated at the preceding dose. If ≤ 1 of 6 subjects experienced a DLT at the preceding dose, then this dose level would be the MTD.
7. If the MTD is not reached, either the maximum dose of 12 mg/kg or a lower dose (OBD) as determined by PK, pharmacodynamic, biomarker, and safety data will be used for cohort expansion.
8. At the discretion of the sponsor, an intermediate dose could have been chosen for dose escalation. Situations that might have prompted selection of an intermediate dose included unexpected toxicities that did not meet the definition of DLT or multiple similar toxicities in a cohort that did not meet the definition of a DLT. If an intermediate dose was chosen, subsequent dose escalation would be to the next predetermined dose provided all the criteria for dose escalation in Rules 2-6 above were met. Further dose escalation would be based on toxicities observed at each dose level, and would be allowed to proceed according to the original dosing schedule or would be allowed to include additional intermediate dosing steps based on accumulated safety data.

Arms B and C

1. The MTD was to be determined based on the assessment of DLT during the DLT period (see Section 4.5.6). Subjects were considered evaluable for assessment of DLT if they completed Cycle 1 of MEDI-551 or discontinued MEDI-551 treatment during Cycle 1 due to a DLT. Non-evaluable subjects were to be replaced. Any MEDI-551 treatment-related toxicity (regardless of grade) leading to an inability to complete the first cycle of MEDI-551 was considered a DLT.
2. If 0 of 3 or ≤ 1 of 6 subjects treated at the previous dose level experienced a DLT, dose escalation was allowed to continue.
3. If ≥ 2 of 6 subjects in a dose cohort experienced a DLT during the DLT period, the MTD would have been exceeded and no further subjects would be enrolled into that dose cohort. If this occurred, the preceding dose cohort would be evaluated for the MTD and a total of 6 subjects would be treated at the preceding dose. If ≤ 1 of 6 subjects experienced a DLT at the preceding dose, then this dose level would be the MTD.

4. If the MTD was not reached, the highest protocol-specified dose will be used for cohort expansion. The highest protocol-specified dose is 48 mg/kg for Arm B and 12 mg/kg for Arm C.

A study-specific Dose Escalation Committee consisting of all study investigators and the sponsor's medical monitor provided ongoing safety surveillance of the study, with regularly scheduled reviews of safety and other relevant data. This committee was responsible for dose-escalation decisions and making recommendations regarding further conduct of the study. The sponsor notified sites when enrollment into each dose cohort had been completed and when enrollment into the next dose cohort was permitted. Details of the composition and role of the Dose Escalation Committee are presented in Section 6.4.

4.5.6 Dose-limiting Toxicities

Dose-limiting toxicities for Arms A, B, and C are described below. This section is not relevant to Arm D.

Arm A

The period for evaluating DLTs was from the time of first administration of MEDI-551 through the first 28-day cycle. Delays of ≤ 5 days within a cycle due to reversible non-DLT toxicities were allowed during the DLT period; in that case, the DLT period was no greater than 33 days. Subjects who did not receive 2 doses (subjects enrolled under protocol Version 5.0) or 4 doses (subjects enrolled under protocol Version 4.0) of MEDI-551 during this time for reasons other than toxicity were to be replaced with another subject at the same dose level. Grading of DLTs was according to the NCI CTCAE V4.03 ([CTCAE, 2010](#)).

A DLT was defined as:

- A MEDI-551 treatment-related AE of any toxicity grade that led to an inability to receive a full cycle of MEDI-551 or
- Any Grade 3 or higher toxicity as described below that could not be reasonably ascribed to another cause, such as disease progression or accident.

During the DLT period, a delay in therapy due to a reversible non-DLT toxicity lasting ≤ 5 days total was not considered a DLT as long as the subject received the full intended dose.

Nonhematologic DLTs were any Grade 3 or higher diagnosis or laboratory finding with the following exceptions:

- Grade 3 fever that lasts \leq 24 hours with or without medical therapy and is not considered an SAE
- Transient Grade 3 rigors or chills that responds to optimum medical therapy
- Grade 3 tumor lysis syndrome that resolves to \leq Grade 2 within 72 hours after initiation of treatment
- Any Grade 3 or 4 electrolyte alteration that is reversible to \leq Grade 1 within 24 hours after it occurs
- Any Grade 3 liver function test elevation that resolves to \leq Grade 1 within 24 hours after it occurs

Grade 3 or higher hematologic toxicities were considered DLTs with the following exceptions:

- \geq Grade 3 lymphopenia or leukopenia in the absence of neutropenia
- \leq Grade 4 neutropenia in the absence of fever that resolves within 5 days
- \leq Grade 4 thrombocytopenia that resolves within 5 days
- \leq Grade 4 anemia in a subject who was transfusion dependent at study entry, or had a history of hemolysis

Arms B and C

The period for evaluating DLTs was from the time of first administration of MEDI-551 through the first 28-day cycle. Grading of DLTs was according to the NCI CTCAE V4.03 ([CTCAE, 2010](#)).

A DLT was defined as:

- A MEDI-551 (or rituximab for Arm C) treatment-related AE of any toxicity grade that led to an inability to receive a full cycle of MEDI-551 (or rituximab for Arm C).
- **NOTE:** During the DLT period, a delay in therapy due to a reversible non-DLT toxicity lasting \leq 7 days total would not be considered a DLT as long as the subject received the full intended dose.

Nonhematologic DLTs were any Grade 3 or higher MEDI-551 (or rituximab for Arm C) treatment-related toxicity not attributable to another cause with the following exceptions:

- Grade 3 fever that lasted \leq 24 hours with or without medical therapy and is not considered an SAE
- Grade 3 rigors or chills lasting $<$ 6 hours that respond to optimum medical therapy

- Grade 3 IRR (first occurrence and in the absence of steroid prophylaxis) that resolves within 6 hours with appropriate clinical management
- Grade 3 tumor lysis syndrome that resolves to \leq Grade 2 within 72 hours after initiation of treatment
- Any Grade 3 electrolyte alteration that is reversible to \leq Grade 1 within 72 hours after it occurs
- Any Grade 3 liver function test elevation up to $8 \times$ ULN and total bilirubin up to $5 \times$ ULN that resolves to \leq Grade 1 within 72 hours after it occurs. Any liver function test elevation $> 8 \times$ ULN or total bilirubin elevation $> 5 \times$ ULN that is attributed to investigational product requires discontinuation of investigational product.

Hematologic DLTs were any Grade 3 or higher MEDI-551 (or rituximab for Arm C) treatment-related toxicity not attributable to another cause, with the following exceptions:

- Grade 3 or 4 neutropenia in the absence of fever or infection that resolves to Grade 2 within 7 days
- Grade 3 or 4 thrombocytopenia that resolves to Grade 2 within 7 days and does not require a transfusion
- Grade 3 anemia that resolves to Grade 2 within 7 days and does not require a transfusion
- Grade 3 or 4 lymphopenia

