1.4 Clinical Experience with MEDI-551

The clinical development of MEDI-551 is ongoing in subjects with B-cell malignancies, systemic scleroderma, relapsing/remitting multiple sclerosis, and neuromyelitis optica (NMO) and NMO spectrum disorders. There are 5 clinical studies of MEDI-551, including MI-CP204, in subjects with B-cell malignancies; these studies are described below, based on a data cutoff date of 31Mar2015.

In the current Phase 1/2 study, MI-CP204, enrollment in the dose-escalation and expansion phases in adult subjects with relapsed and refractory advanced B-cell malignancies (CLL, DLBCL, FL, or MM) has been completed (enrollment of MM subjects was discontinued

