after the start of the dose-expansion phase due to lack of activity based on nonclinical and preliminary clinical data). Subjects in the dose-escalation phase received MEDI-551 at doses of 0.5, 1, 2, 4, 8, or 12 mg/kg (3 to 6 subjects per dose cohort), or 12 mg/kg (a total of 75 subjects in the combined dose-escalation and dose-expansion portions of this arm of the study received 12 mg/kg). Two dose-limiting toxicities (DLTs) were reported as infusion-related reactions; one occurred at the 4 mg/kg cohort and the other at 12 mg/kg dose level. The protocol was amended to add 3 arms to the study: Arm B applies dose escalation to determine the maximum tolerated dose (MTD) or maximum dose that will saturate the B-cell sink in subjects with CLL; Arm C combines rituximab and MEDI-551 in treating subjects with aggressive lymphomas; and Arm D assesses the activity of MEDI-551 monotherapy in subjects with anti-CD20- refractory aggressive lymphomas. The protocol was further amended to include mandatory steroid prophylaxis and graded infusions consistent with Studies CD-ON-MEDI-551-1019 and CD-ON-MEDI-551-1088 (see below). A total of 111 subjects have been treated with MEDI-551 in MI-CP204. The most commonly reported adverse events (AE) (> 20% of subjects) were infusion-related reaction, fatigue, cough, and nausea. The most commonly reported related AEs (in $\geq 5\%$ of subjects in the overall study population) were infusion-related reaction, nausea, neutropenia, fatigue, and vomiting. Deaths were reported for 27 of 111 (24.3%) subjects in MI-CP204. Progressive disease (PD) was the most common cause. All 27 deaths were considered unrelated to MEDI-551. Twenty-eight subjects (25.2%) in MI-CP204 experienced serious adverse events (SAEs); SAEs were noted in every dose cohort except the 2 dose cohorts in Arm B (6 mg/kg or 12 mg/kg every week for 4 weeks, then every 4 weeks, N = 6 for the combined cohorts). In Study MI-CP204, mean serum MEDI-551 PK concentration-time profiles following IV administration declined in a bi-exponential manner, with an initial rapid distribution followed by a slower elimination phase. In general, MEDI-551 PK was dose proportional between 0.5 and 12 mg/kg following the first dose. Thirty of 111 subjects (27.0 %) in MI-CP204 experienced objective response (OR), defined as complete response (CR) or partial response (PR). Three subjects, 2 subjects who achieved CR and 1 subject who achieved a very good PR, were retreated following relapse.

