14. Use of systemic steroids within 7 days before the first dose of MEDI-551 (inhaled and topical corticosteroids are permitted). Subjects may take replacement doses of steroids (defined as \leq 30 mg/day hydrocortisone or the equivalent) if on a stable dose for at least 2 weeks prior to the first dose of MEDI-551. This does not include required steroid prophylaxis prior to the first infusion of MEDI-551
15. Documented current central nervous system involvement by leukemia or lymphoma
16. Pregnancy or lactation
17. Previous medical history, or evidence, of an intercurrent illness that at the discretion of the principal investigator may compromise the safety of the subject in the study
18. Clinically significant abnormality on electrocardiogram (ECG). The corrected QT interval (QTc, Fridericia) must be $<$ 470 milliseconds for men and $<$ 490 milliseconds for women (Must be confirmed by at least 2 additional 12-lead ECGs at least 2 minutes apart such that average manually over-read QTcF based on 3 ECGs exceeds stated thresholds)
19. Any physical, social, or psychiatric condition that would prevent effective cooperation or participation in the study
20. Concurrent enrollment in another clinical study, unless in a follow-up period or it is an observational study
21. Employees of the clinical study site who are directly involved with the conduct of the study, or immediate family members of such individuals. These subjects may be treated at another site participating in the study
22. History of other invasive malignancy within 5 years except for localized/in situ carcinomas.

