All subjects must receive mandatory premedication consisting of a minimum dose of 60 mg of IV methylprednisolone (or its equivalent) as well as 500 to 650 mg oral acetaminophen (or

paracetamol equivalent) and 50 mg IV diphenhydramine (or its equivalent) before the start of the initial MEDI-551 infusion. The initial infusion of MEDI-551 will be administered a minimum of 30 to 60 minutes after administration of mandatory premedications (as described in this section) according to the following sequence of infusion rates, regardless of dosage form:

- 1 mL/minute for a minimum of 15 minutes, then
- 2 mL/minute for a minimum of 15 minutes, then
- 4 mL/minute to complete the infusion

The minimum infusion time will be 81 minutes. Subjects receiving doses ≥ 24 mg/kg in Arm B will receive the initial infusion over 2 days on Day 1 and Day 2 of Cycle 1. The Day 1 infusion will be administered over a minimum of 81 minutes as described above. The Day 2 infusion will be administered over a minimum of 60 minutes (+ 15 minutes at the investigator's discretion). If the subject experiences an infusion reaction on Day 1, the Day 2 infusion will be administered over a minimum of 90 minutes. Subjects will be monitored closely during the initial infusion of MEDI-551, with vital signs recorded every 5 minutes over the first 30 minutes of the infusion and then every 15 minutes for the remainder of the infusion duration. Additional details regarding vital signs monitoring during the initial infusion of MEDI-551 are provided in Section 6.4.3. For subsequent infusions, MEDI-551 will be administered over 60 minutes (+ 15 minutes at the investigator's discretion). Vital signs will be monitored as described in Section 6.4.3. The initial infusion of MEDI-551 will be administered on Day 1 of Cycle 1 for Arms B and D, and Day 2 of Cycle 1 for Arm C.

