Section 6.4.2 (Study Stopping Criteria)

This section was revised to be consistent with the new protocol template (v16.2).

Sections 6.4.3 (Monitoring of Dose Administration)

This section was revised to reflect Arm D, which will follow the same monitoring procedures as Arms B and C.

Section 7.3 (Endpoints)

The primary, secondary, and exploratory endpoints of Arm D were added.

Section 7.4.3 (Efficacy Assessments)

The definition of MRD-negative CR was added to efficacy assessments.

Section 7.5 (Sample Size and Power Calculations)

Sample size and power calculations were added for Arm D.

Section 14 (References)

New references cited in the protocol were added to the reference list.

Protocol Version 12.0, 27Jan2015

Version 11.0 of protocol MI-CP204, dated 21Mar2014, has been amended to create Version 12.0, dated 12Jan2015. The purpose of the amendment is to add information regarding the [REDACTED] dosage strength and to remove references to the [REDACTED] dosage strength of MEDI-551. Modifications to CT/PET scan frequency were made to minimize radiation exposure. In Arm B, subjects receiving doses ≥ 24 mg/kg will receive the initial weekly doses in Cycle 1 over Days 1-2 as mitigation for infusion-related reactions.

This is being implemented in addition to existing safeguards of prophylactic medications (including antihistamines and corticosteroids) and the option to decrease infusion rate because 2 out of 3 subjects at the 6 mg/kg dose level experienced Grade 3 infusion-related reactions during the first infusion.

An allowance for prophylaxis against tumor lysis syndrome in subjects with large tumor burden was added. Appendix 2, Rituximab Prescribing Information, was updated. Other changes were made for clarity and consistency. In addition, changes from Administrative Change 1, dated 30Jun2014, were incorporated. All text revisions resulting from this amendment are incorporated in the body of protocol Version 12.0. Major changes to the protocol are described below.

1. Cover page – Change in medical monitor.
2. Study Abstract – The abstract was modified to mirror the changes made to the protocol body.
3. Section 3.1 (Overview of Study Design) – Language was added to describe the dosing schedule for subjects in Arm B receiving 24 or 48 mg/kg dose levels of MEDI-551. The initial doses will be administered over 2 days on Day 1 and Day 2 in Cycle 1. The flow diagram for Arm B was updated to be consistent with this change.

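### Arm B, 6 mg/kg: two Grade 3 first-infusion reactions appear to have been scored as non-DLTs with no stated basis; the DLT table in Section 7.4.1 needs that basis, and its wording on the highest dose needs correcting

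*Protocol*

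**What the plan says.** **DLT definition.** Protocol Section 4.5.6 (Arms B and C) makes treatment-related Grade 3 or higher nonhematologic toxicity a DLT, with listed exceptions. One is "Grade 3 IRR (first occurrence and in the absence of steroid prophylaxis) that resolves within 6 hours with appropriate clinical management". Two others carry no steroid condition: "Grade 3 fever that lasted" no more than 24 hours and was not an SAE, and Grade 3 rigors or chills of under 6 "hours that respond to optimum medical therapy". A related event of any grade that prevents a full first cycle is also a DLT.

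**Steroid mandate.** Section 4.5.3 (Arms B, C and D) states "All subjects must receive mandatory premedication consisting of a minimum dose of 60 mg of IV methylprednisolone (or its equivalent", with acetaminophen and diphenhydramine, before the initial MEDI-551 infusion. Sections 4.5.4 and 6.4.3 repeat this. Exclusion criterion 14 in Section 4.2.2 uses the same term as the DLT exception: "This does not include required steroid prophylaxis prior to the first infusion of MEDI-551".

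**Events and conduct.** The Version 12.0 entry in Section 15 reports that "2 out of 3 subjects at the 6 mg/kg dose level experienced Grade 3 infusion-related reactions during the first infusion". Section 7.5 gives Arm B enrollment as three subjects at 6 mg/kg, three at 12 and one at 24, and says the MTD was not reached. Under rule 2 for Arms B and C in Section 4.5.5, escalation needs 0 of 3 or at most 1 of 6 with a DLT. Rule 3 treats 2 or more of 6 as exceeding the MTD.

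**Reporting.** Section 7.4.1 will present DLT counts by dose level. It also says that, with no MTD reached, the highest protocol-defined dose for Arms B and C was determined from all available data. Rule 4 in Section 4.5.5 sets that dose at 48 mg/kg for Arm B. Section 3.1 says the 48 mg/kg cohort was not enrolled.

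**The concern.** A reader who applies the current IRR exception to the two reported events, assuming the mandated steroid was given, scores 2/3 DLTs at the Arm B starting dose. The escalation implies 0/3. The protocol does not reconcile the two counts. DLTs, with the MTD or the highest protocol-specified dose, form the first primary endpoint of Arm B (Section 7.3.1), and the statement that no MTD was reached depends on how these two events are classified.

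Section 7.4.1 adds a smaller problem. Its wording suggests that a highest protocol-defined dose was established for Arm B, when the dose so defined was never given.

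**Working it through.** **1. The escalation rule reproduces the plan's own table.** If a cohort passes on 0/3, or on 1/3 followed by 0/3, then P(escalate) = (1-p)^3 + 3p(1-p)^2 x (1-p)^3.

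| True DLT rate | Table 7.5-1 | Recomputed |
|---|---|---|
| 10% | 0.91 | 0.906 |
| 20% | 0.71 | 0.709 |
| 30% | 0.49 | 0.494 |
| 40% | 0.31 | 0.309 |
| 50% | 0.17 | 0.172 |
| 60% | 0.08 | 0.082 |
| 70% | 0.03 | 0.032 |
| 80% | 0.009 | 0.0088 |
| 90% | 0.001 | 0.001 |

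All nine entries match. The table sits under Arm A, but rule 2 for Arms B and C passes a cohort on the same counts. There is no error in the escalation arithmetic.

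**2. What was scored at 6 mg/kg.** The cohort stopped at 3 and 12 mg/kg was opened, so rule 2 implies 0/3. Section 1.4 agrees: of the two IRR DLTs it reports, "one occurred at the 4 mg/kg cohort and the other at 12 mg/kg dose level". That sentence follows the Arm A description, so its scope is arguable, but no DLT at 6 mg/kg is listed. Section 1.4 has a data cutoff of 31Mar2015, after Version 12.0 (27Jan2015) had reported the events.

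**3. Which definition governed.** Arm B was added by Version 10.0 (07Oct2013) and the events appear in Version 12.0. Both subjects were therefore dosed under Version 10.0 or 11.0 (21Mar2014). The log says Version 10.0 added the Arm B and C DLT criteria and lists no later change to Section 4.5.6. It lists major changes only, so this is good but not conclusive evidence that the exception read then as it does now.

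**4. Whether steroids were given.** This is not stated. The Version 12.0 entry calls corticosteroids an existing safeguard and speaks of reiterating mandatory premedication. The same entry says text was added to Section 4.5.4 to recommend it. Section 1.4 says only that the mandate came by a further amendment.

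**5. Possible table entries** (exact Clopper-Pearson 95% limits, n = 3):

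| DLTs at 6 mg/kg | Rate | 95% limits | If three more were added | Consequence |
|---|---|---|---|---|
| 0/3 | 0% | 0-70.8% | not needed | escalation supported |
| 1/3 | 33% | 0.8-90.6% | 1/6 to 4/6 | expansion to 6 was due first; neither cleared nor exceeded |
| 2/3 | 67% | 9.4-99.2% | 2/6 to 5/6 | always at least 2 of 6, so MTD exceeded (rule 3) |

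Arm B subjects treated above 6 mg/kg: 3 + 1 = 4 of 7.

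**6. A cross-check.** Rule 1 counts a subject as evaluable only on completing Cycle 1 or stopping in Cycle 1 for a DLT, and non-evaluable subjects were to be replaced. With three enrolled and none replaced, 0/3 means all three completed Cycle 1. Table 4.5.2.1-2 calls for discontinuation after a Grade 3 infusion reaction despite steroid prophylaxis, although Section 6.4.1 also lets reactions that respond and are of limited duration continue. Cycle 1 completion is therefore informative.

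**The case against.** The strongest reply is that Section 4.5.6 is neither empty nor contradictory. The steroid is mandatory only before the initial infusion. After a Grade 1 or 2 reaction it is discretionary (Section 4.5.3), so the exception can operate later in Cycle 1, for example on Days 8, 15 and 22 in Arm B. Counting a Grade 3 reaction despite steroids as a DLT also fits the discontinuation rule. This stands: the definition answers the question and needs no rewording.

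A reader might go further and infer that the MTD was exceeded at 6 mg/kg, or that the sponsor misclassified the events. The documents do not support either. The DLT text of Versions 10.0 and 11.0 is not shown, and neither the subjects' steroid exposure nor their times to resolution are given. The mandate may have followed their dosing. The fever or rigors/chills exceptions might apply. Section 1.4 reports no SAEs in the Arm B 6 and 12 mg/kg cohorts, which is compatible with short, manageable reactions.

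It can also be said that classification belonged to the investigators' data review, which required unanimity and a written outcome, and that table footnotes belong in the SAP or study report. The written outcome is indeed where to look. But the definition, the escalation rule, the events and the MTD conclusion all stand in this protocol, and they do not fit together without a stated reason.

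**Conclusion.** The point holds as a reporting correction of minor to moderate weight. The IRR exception cannot reach a first MEDI-551 infusion given with the mandated steroid. Two Grade 3 first-infusion reactions occurred among three subjects, the escalation implies 0/3, and no basis is given. The classification of two events decides whether the 6 mg/kg entry is 0/3, 1/3 or 2/3. Only 2/3 contradicts the statement that no MTD was reached; 1/3 would be a deviation from the escalation rule and would not show the MTD exceeded.

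This rests on two inferences: that escalation followed rule 2, so both events were scored as non-DLTs, and that the exception was worded in Versions 10.0 and 11.0 as it is now. Misclassification is not established. Enrollment is closed and Arm B was not expanded, so no dosing decision remains open.

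Separately, Section 7.4.1 is inaccurate for Arm B whatever the record check shows. No subject received 48 mg/kg; escalation ended at the sponsor's discretion after one subject at 24 mg/kg.

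**What to change.** 1. Leave the Section 4.5.6 definition unchanged. It is answerable as written and should not be altered after enrollment has closed.
2. Before finalising the Section 7.4.1 DLT table, check both 6 mg/kg events against the DLT definition in force on the dosing date (Version 10.0 or 11.0). Cover whether a steroid was given, time to resolution, the fever and rigors/chills exceptions, Cycle 1 completion, and the written outcome of the escalation meeting.
3. Report the resulting count with a footnote giving its basis:
   - 0/3: the escalation is supported.
   - 1/3: a deviation, since escalation preceded the required expansion to six; the MTD is not shown to be exceeded.
   - 2/3: the MTD was exceeded at 6 mg/kg, and the statement that it was not reached must be withdrawn for Arm B.
4. Correct Section 7.4.1 to say that Arm B's highest protocol-defined dose (48 mg/kg) was not evaluated and that escalation stopped at the sponsor's discretion after one subject at 24 mg/kg.

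The cost is a review of two subject records and one existing meeting record, one table footnote and one wording change. No new data or subjects are needed. The Arm B conclusion becomes less favourable only if an event proves not to be exempt.
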